7.2 Analysis Visits Windows

Subjects do not always adhere strictly to the visit schedule timing in the protocol. Therefore, the designation of visits during the study period will be based on the day of evaluation relative to the Day 1 of the trial (day of first dosing = study Day 1) rather than the nominal visit recorded in the case report form (CRF). Visit window based on the study day (regardless the visit labeling) will be applied for efficacy analysis and safety analysis. Each efficacy and safety measurement will be windowed. In case that two or more measurements exist in a certain visit window, the one closest to the target day will be selected. If still more than one measurements are selected, the later one will be selected for analysis.

Efficacy measurements up to last dose will be used for windowing.

Analysis Visit	Target Day	Study Day Range
Baseline	1	[-28, 1]
Week 2	15	[2, 22]
Week 4	29	[23, 43]
Week 8	57	[44, 71]
Week 12	85	[72, 99]
Week 16	113	[100, 127]
Week 20	141	[128, 155]
Week 24	169	[156, 183]
Week 28	197	[184, 211]
Week 32	225	[212, 239]
Week 36	253	[240, 267]
Week 40	281	[268, 295]
Week 44	309	[296, 323]
Week 48	337	[324, 351]
Safety Follow-up	EOT + 30	

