11.7 Efficacy Analyses

All efficacy analyses will be performed using the randomized population.

The final statistical analysis will be performed at the end of study after all subjects have completed their end of study visit (or discontinued early from the study).

Separate methods will be used for binary, continuous, time-to-event and categorical efficacy endpoints.

Subjects listings will report all collected efficacy endpoints over time until study end or early study discontinuation, regardless of treatment discontinuation before the study end or discontinuation.

Binary endpoints for analysis are:

- SRI(4) [REDACTED]
- BICLA response
- LLDAS response
- CLASI-A response

Continuous endpoints for analysis are:

- Change from baseline in the 40-joint count for tender joints, swollen joints, and joints that are both tender and swollen (= active joints)
- Global BILAG-2004 score

Categorical endpoints:

[REDACTED]

Sponsor: Bristol-Myers Squibb
Protocol no: IM011021

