The number and percentage of subjects achieving NRI-imputed SRI(4) response at Week 32 and those who do not will be reported by treatment group with the estimated response rate and asymptotic 95% confidence intervals (CIs). Differences in response rates between each active treatment group and placebo with corresponding 2-sided 95% CIs based on the continuity-corrected Newcombe method will also be provided.

Tipping Point Analysis

Tipping point analysis will further be used to assess the robustness of the primary study results. Different number of events between treatment groups will be assessed until the study conclusion is

Sponsor: Bristol-Myers Squibb
Protocol no: IM011021

changed. Each imputed value is initially imputed as a responder. The imputed values in the placebo group will remain as responders while the BMS-986165 imputed values are replaced as a non-responders one at a time, therefore changing the number of events between groups. Once all imputed values in the BMS-986165 group have been replaced with non-responders values, the data will reset to where the BMS-986165 group imputed values are all responders and one by one the imputed values in the placebo group are replaced with a non-responder until all placebo are non-responders and all BMS-986165 are responders. Furthermore, every pair of imputations between the placebo and BMS-986165 groups will be assessed similarly, creating a matrix of possible patterns.

At each iteration, the statistical analysis is assessed, and the direction of the analysis is recorded. A graph will be provided to identify at what point to which the difference in events cause a direction shift in study results. The tipping point analyses will be based on a two-sample chi-square test approach rather than a stratified CMH test approach for simplicity of the analysis.

Sensitivity analysis #1 (Treatment Policy Strategy)

The primary analysis for the primary endpoint will be repeated using a treatment policy estimand approach (Intention-To-Treat (ITT) principle). For this approach, subjects will only be imputed as non-responders if there is a missing value for the endpoint at the considered timepoint.

Sensitivity analysis #2

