The primary analysis for the primary endpoint will be repeated, however the NRI imputation method will be modified. The prohibition medications restriction for the NRI imputation method will not apply. That is, subjects who take any of the prohibited medications listed above will not be imputed as non-responders. Subjects will continue to be imputed as non-responders if any of the following apply:

- Permanent treatment discontinuation of IP before the considered time point
- Missing value for the endpoint at the considered time point
- Subjects who are lost to follow-up or discontinue the study early are considered non-responders for all time points at and after loss to follow up or study discontinuation

Supportive Analysis #1 – Assessment of Covid-19 related impact

For this supportive analysis, the primary analysis for the primary endpoint will be repeated, but observations that were missed due to the impact of COVID-19 will be imputed with the last value observed before the visit that was missed due to COVID-19 restrictions.

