11.7.2 Secondary Endpoints

11.7.2.1 SRI(4) Response at Week 48

SRI(4) response at week 48 is defined in an analogous way as SRI(4) response at week 32 (see details in 12.7.1).

Similar analyses will be conducted as for the primary endpoint, including the primary analysis and sensitivity analysis.

Sponsor: Bristol-Myers Squibb
Protocol no: IM011021

11.7.2.2 BICLA Response at Week 48

All subjects in the randomized population will be categorized as a responder or non-responder. A subject will be considered a BICLA Week 48 responder if all of the following criteria are met. If one criterion is not met, the subject will be considered a BICLA Week 48 non-responder.

- Improvement in all organ systems with activity graded as BILAG-2004 A or B at baseline
 - This criterion is met if both of the following conditions are met: All organ domains with an A grade at baseline are graded B, C, D, or E at Week 48
 - All organ domains with an B grade at baseline are graded C, D, or E at Week 48
- No new organ system with activity graded as BILAG A and no more than 1 new organ system with activity graded as BILAG B
An A grade is new if the baseline grade for the same organ system was B, C, D or E. A B grade is new if the baseline grade for the same organ system was C, D, or E.

This criterion is met if both of the following conditions are met:

- There are no organ domains with an A grade at Week 48
 - The number of organ domains with a B grade at Week 48 that were graded C, D, or E at baseline is ≤ 1
- No increase from baseline in SLEDAI-2K (≤ 0 points for change from baseline score)
SLEDAI-2K score at Week 48 - SLEDAI-2K score at baseline ≤ 0
 - No increase $\geq 10\%$ (or ≥ 0.3 points) in the Physician's Global Assessment of Disease Activity on a 3-point VAS:
Physician's Global Assessment of Disease Activity at Week 48 – Baseline Physician's Global Assessment of Disease Activity < 0.3
 - No discontinuation of IP or use of prohibited/restricted medications beyond the protocol allowed threshold before assessment.

- No discontinuation of IP is defined as remaining on IP within 14 (≤ 14) days prior to the Week 48 visit. Treatment discontinuation date is captured in the eCRF.
- Restricted/prohibited medications are defined as in [section 11.7.1](#) and are:
 - Corticosteroid dosages above 7.5mg/day prednisone or equivalent after week 20 (Week 20+1 day)
 - Use of IM or IV CS within 8 weeks before the W32 and W48 assessment timepoints

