Analyses of each of these three endpoints will be conducted using a mixed model repeated measures (MMRM) model. For analysis visits where the NRI-imputation criteria are met (see [section 11.7.1](#)), no imputation is applied but the observed values are set missing. The MMRM model will include the fixed categorical effects of treatment group, analysis visit (Week 24, 32 and 48), treatment-by-analysis visit interaction, randomization stratum defined in [section 6.5](#) and the continuous fixed covariate of baseline endpoint. An unstructured covariance matrix will be used to model the correlation of the repeated measures within each subject. The parameter estimations will be based on the assumption of data being missing at random (MAR) and using the method of restricted maximum likelihood (REML). The denominator degrees of freedom will be calculated using the Kenward-Rogers method. Adjusted mean changes (LSMEANS) with corresponding SE and 95% CI per treatment arm will be reported. The difference in adjusted means (LSMEANS) between BMS-986165 and placebo at the predefined time point, and corresponding 95% CI and p-value based on this longitudinal repeated measures model will be provided. In case of non-convergence of the preferred longitudinal model, memory space issues, or other computational issues the following covariance structures will be used in order of preference (decreasing number of parameters to be estimated): heterogeneous toeplitz, heterogeneous compound symmetry, and compound symmetry.

A longitudinal plot of mean change from baseline in tender joint count, swollen joint count, and tender +swollen joint count with standard errors by treatment group will be provided.

[figure not shown]
A sensitivity analysis will be conducted similar to the primary endpoint (treatment policy strategy).

Sponsor: Bristol-Myers Squibb

Protocol no: IM011021

[figure not shown]
Sponsor: Bristol-Myers Squibb
Protocol no: IM011021

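### The last-dose cut in SAP 7.2 removes post-discontinuation assessments from the treatment-policy analyses that are meant to use them

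*SAP*

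**What the plan says.** **Windowing.** SAP 7.2 applies study-day windows to efficacy and safety data, then restricts efficacy: "Efficacy measurements up to last dose will be used for windowing". SAP 7.1 takes the last dose date from the End of Treatment eCRF form. SAP 11.0 makes the 7.2 analysis visits the default for reporting.

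**Treatment-policy analysis of the primary endpoint.** SAP 11.7.1 labels sensitivity analysis #1 treatment policy, following the ITT principle, and says "subjects will only be imputed as non-responders if there is a missing value for the endpoint at the considered timepoint". It does not mention the 7.2 cut. Sensitivity analysis #2 drops the prohibited-medication rule but keeps this non-response trigger: "Permanent treatment discontinuation of IP before the considered time point".

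**Week 48 endpoints.** For SRI(4), and in the same sentence for CLASI-50 and LLDAS, SAP 11.7.2 says: "Similar analyses will be conducted as for the primary endpoint, including the primary analysis and sensitivity analysis". For the joint counts, SAP 11.7.2.5 names the approach directly: "A sensitivity analysis will be conducted similar to the primary endpoint (treatment policy strategy". That model uses Weeks 24, 32 and 48 and assumes data are missing at random (MAR).

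**Off-treatment data.** Protocol 7.1 and 7.2 keep subjects who stop treatment in the study. Protocol Table 3 and SAP Appendix 2 schedule BILAG, SLEDAI-2K, Physician's Global Assessment, joint count and CLASI at the follow-up visit, which Table 3 limits to subjects not entering the extension study. SAP 11.7 says: "Subjects listings will report all collected efficacy endpoints over time until study end or early study discontinuation, regardless of treatment discontinuation". That sentence covers listings only.

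**The concern.** Sensitivity analysis #1 is the planned check on whether the SRI(4) result depends on counting IP discontinuation as failure. To do that it must use what was observed after subjects stopped. The 7.2 cut turns those observations into missing values, and the missing-value rule then turns them into non-response. The check therefore reproduces the assumption it is meant to relax.

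The cut does little elsewhere. The primary NRI analysis and sensitivity analysis #2 already make discontinuation a non-response, and the main joint-count model already sets values to missing when an NRI criterion is met. Its practical effect falls on the treatment-policy analyses.

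The tipping point analysis does not fill the gap. The SAP introduces it with "Tipping point analysis will further be used to assess the robustness of the primary study results". It varies hypothetical outcomes, does not use observed off-IP data, and is stated for the primary result and not for the Week 48 endpoints.

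**Working it through.** The documents give no figure to reproduce here. The check is a comparison of rules, followed by a size estimate under stated assumptions.

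**1. The rules applied to one subject.** A subject permanently stops IP before Week 32 and is assessed inside the Week 32 window (Days 212-239).
- SAP 7.2: the assessment is after last dose, so it is not windowed and the Week 32 value is missing.
- Sensitivity analysis #1: missing value, so non-responder.
- Sensitivity analysis #2: discontinued before the time point, so non-responder.
- Treatment policy as labelled: the observed outcome should count.

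**2. Enumeration.** Take every last-dose day from 1 to 336, with assessments on the target days (225 and 337) and full follow-up.

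| | Week 32 | Week 48 |
|---|---|---|
| Days on which #1 under 7.2 differs from #2 | 0 of 336 | 0 of 336 |
| Days on which lifting the cut makes a value usable | 224 of 336 | 336 of 336 |

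#1 and #2 can differ for a discontinuer only if an in-window assessment precedes a last dose that itself falls before the target day, for example assessed on Day 215 with last dose on Day 220.

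**3. How often the scheduled follow-up visit lands in a window.** Table 3 puts it 28 days after end of treatment (EOT).
- Week 32 window, Days 212-239: EOT on Days 184-211. If stopping is uniform over Days 1-224, 28/224 = 12.5% of stoppers. With the EOT + 30 target in SAP 7.2 the range is Days 182-209, again 12.5%.
- Week 48 window, Days 324-351: EOT on Days 296-323, 28/336 = 8.3%.
- Week 24 window, Days 156-183: EOT on Days 128-155, 28 days.
- Weeks 24, 32 and 48 together: 84/336 = 25% of possible EOT days.

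**4. Responders overwritten at Week 32.** Assumptions: 10-20% of 90 per arm stop before Week 32 (9-18 subjects), and 30% of those assessed off IP would be responders. With f the fraction of stoppers assessed in the window, the number overwritten per arm is 90 × (0.10 to 0.20) × f × 0.30.

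| Scenario | f | Subjects per arm | Percentage points |
|---|---|---|---|
| (a) Follow-up visit only | 0.125 | 0.34-0.68 | 0.38-0.75 |
| (a) plus off-IP EOT visits, last dose Days 212-224 | 41/224 = 0.183 | 0.49-0.99 | 0.55-1.1 |
| (b) Half of stoppers assessed | 0.5 | 1.35-2.7 | 1.5-3.0 |
| (c) All stoppers assessed | 1 | 2.7-5.4 | 3.0-6.0 |

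With 20-40% responders, (a) becomes 0.25-1.0 points and (c) becomes 2-8 points.

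**5. Effect on the treatment difference.** It is 0 if stopping, assessment and off-IP response are equal across arms. With 10% stopping in one arm and 20% in the other, the shift is 100 × 0.30 × f × 0.10, which is 0.38 points in (a) and 3.0 points in (c). The design difference is 20 points.

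An illustration of (c) with assumed on-treatment response of 40% on placebo and 60% on active, and stopping of 25% and 15%:
- Under 7.2 as written: 0.85 × 60 − 0.75 × 40 = 21 points.
- Using off-IP outcomes at 30% response: 21 + 30 × (0.15 − 0.25) = 18 points.

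**6. Week 48.** The same stopping rate carried to Day 336 gives 15-30%.
- SRI(4), follow-up visit only: 90 × (0.15 to 0.30) × 28/336 × 0.30 = 0.34-0.68 subjects per arm, or 0.38-0.75 points.
- Joint counts: 90 × (0.15 to 0.30) × 84/336 = 3.4-6.8 subjects per arm have a follow-up visit in a modelled window that the cut leaves missing.

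**The case against.** **The specific rule may be meant to govern.** SAP 7.2 is a general convention, while 11.7.1 defines sensitivity analysis #1 by name with its own single trigger for non-response. A reader could infer that the cut does not apply there. No visible text says so, and a programmer following 7.2 would apply it.

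**Parts of the SAP are redacted or not shown.** An exception there cannot be excluded. This stands as a limit on confidence.

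**Off-IP collection is only partly documented.** Table 3 shows no separate off-treatment schedule for Weeks 32 and 48, and the relevant sentence in Protocol 7.3 is partly redacted. Scenarios (b) and (c) are therefore assumptions. Scenario (a) also assumes that every stopper attends follow-up, which withdrawal, loss to follow-up or entry into the extension would reduce. This stands as to size, and the effect may be small.

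**The extension to Week 48 SRI(4), CLASI-50 and LLDAS is inferred.** Their sections refer to sensitivity analysis in the singular, although two are defined. Treatment policy is named only for Week 32 SRI(4) and the joint counts. That is fair, but repeating the primary endpoint's sensitivity analysis is the natural reading.

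**No primary result changes, and sensitivity analysis #1 is not empty.** Both are true: it still follows treatment policy for prohibited medication. But the discontinuation part of the check is lost.

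**Conclusion.** The point holds and should be fixed. As written, SAP 7.2 defeats the treatment-policy analyses for permanent IP discontinuation: Week 32 SRI(4), its Week 48 counterparts for SRI(4), CLASI-50 and LLDAS, and the joint counts. The conflict lies in the text and does not depend on how many subjects are involved. Confidence is medium because of the redactions.

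The numerical effect is uncertain. It depends on assumed stopping rates, off-IP response and attendance, none of which the documents give. On the visible follow-up schedule alone it is below about 1 point per arm. It reaches several points only if most stoppers are assessed in the window.

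BICLA is a separate, smaller matter. Staying on IP is part of its definition, so later data cannot create a BICLA response more than 14 days after last IP. However, SAP 11.7.2.2 accepts a Week 48 visit up to 14 days after last IP, whereas 7.2 excludes data from visits 1-14 days after last dose.

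**What to change.** - In SAP 7.2, limit the last-dose cut to the NRI and on-treatment analyses.
- State in 7.2 and 11.7 that sensitivity analysis #1 (Week 32 SRI(4); Week 48 SRI(4), CLASI-50 and LLDAS) and the treatment-policy joint-count analysis window all efficacy measurements collected through end of study by study day, including EOT and follow-up visits, whatever the last dose date.
- For BICLA, only reconcile the 7.2 cut with the 14-day rule in 11.7.2.2. Leave the general NRI discontinuation criterion unchanged.

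The cost is a few SAP sentences, a second windowing flag in the analysis dataset and a little more programming. No new data are collected and the primary estimand does not change.

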8.0 Populations for Analyses

The following populations will be used in the summary and analysis of study data.

8.1 Enrolled

The Enrolled population is defined as all subjects who signed informed consent.

8.2 Randomized

The Randomized population is defined as all subjects who are randomized to a treatment. Subjects will be analyzed as per randomized treatment according to the IRT.

Sponsor: Bristol-Myers Squibb
Protocol no: IM011021

8.3 All-treated

The All-treated population consists of all randomized subjects who receive at least one dose of any study treatment. A subject will be considered to have received their randomized treatment unless they receive the incorrect treatment for the entire duration of the double-blind treatment period.

8.4 Biomarker

The Biomarker population is defined as all randomized subjects who receive at least one dose of study treatment and have at least one post-treatment biomarker measurement. Subjects will be analyzed according to the treatment received.

8.5 Pharmacokinetic

The Pharmacokinetic (PK) population is defined as all randomized subjects who receive at least one dose of BMS-986165 and have any available concentration data. The evaluable PK population is a subset of the PK Population that includes all subjects who have adequate PK profiles or have at least one evaluable PK parameter.

The bioanalytical lab will receive the true randomization file and will only analyze the plasma samples from the subjects who received BMS-986165 drug. Subjects will be analyzed according to the treatment received.

9.0 Analysis and Reporting

The final (and only) database lock will occur once all randomized subjects have completed 48 weeks of double-blind treatment (or have discontinued earlier) and the 4-week safety follow-up for those who have not enrolled into the LTE study IM011074.

10.0 Data Review

10.1 Data Handling and Transfer

Data will be entered and exported as SAS® version 9.4 or higher datasets. Converted datasets will be created using SAS® and following standard Clinical Data Interchange Standards Consortium Standard Data Tabulation Model (CDISC SDTM, version 1.4 or higher, Implementation Guide version v3.2 or higher) conventions. Analysis datasets will be created using SAS® and following CDISC Analysis Data Model (ADaM, version 2.1 or higher, Implementation Guide 1.1 standards or higher).

Additional details can be found in the [REDACTED] Data Management Plan for this study.

11.0 Statistical Methods

Unless otherwise noted, variables will be reported using summary statistics according to the below methods by treatment group and analysis visit defined in [section 7.2](#).

Categorical variables will be summarized using frequency distributions (counts and percentages). Percentages will be rounded to one decimal place, and percentages will not be displayed for zero counts.

For continuous variables summary statistics will include the number of observations (n), mean, standard deviation (SD), median, minimum, maximum, 25th percentile (Q1), and 75th percentile (Q3). The median, minimum, maximum, Q1, and Q3 values will be displayed to the same level of precision as the raw data, the mean to a further decimal place and the SD to two additional decimal places.

P-values will be displayed to 3 decimal places, with values less than 0.001 presented as <0.001.

All data will be listed by subject, analysis visit and treatment group.

All statistical analysis and reporting will be done using SAS® Version 9.4 or higher (SAS Institute, Inc.).

Sponsor: Bristol-Myers Squibb
Protocol no: IM011021

11.1 Subject Disposition

The number of subjects enrolled/screened, reasons of screen failure and the number and percentage of subjects randomized, treated, and in each analysis population will be presented.

Additionally, the following summaries will be provided by treatment group and overall:

- Number and percentage of subjects enrolled, randomized and treated by geographic region (North America, Latin America, Japan, rest of world), country, and center
- Number and percentage of subjects who completed the study, discontinued the study, reason for study discontinuation, completed the treatment phase, discontinued treatments, and reason for treatment discontinuation
- Number and percentage of subjects on treatment at each analysis visit

Subject disposition data will be taken from the End Of Treatment and End Of Study CRF forms.

11.2 Demographic and Baseline Characteristics

Demographic characteristics will be reported by treatment group for both the randomized, and all-treated populations using summary statistics. Demographic characteristics include the following:

- Geographic Region (North America, Latin America, Japan, rest of world)
- Sex
- Race
- Ethnicity
- Age (in years, at time of signing informed consent) and age category (<65 vs \geq 65)
- Baseline CS Use (yes, no)
- Baseline Anti-malarial Use (yes, no)
- Baseline Immunosuppressant Use (yes, no)

- Oral CS Dose (observed dose as categories in mg/day, prednisone or equivalent)
- Oral CS Dose (\geq 10 mg/day vs < 10 mg/day; prednisone or equivalent)
- Weight (in kg)
- Height (in m)
- Body mass index (BMI in kg/m²)
- Number and percentage of subjects within each geographic region categorized by baseline CS dose (\geq 10 mg/day or < 10 mg/day) and baseline SLEDAI-2K score (\geq 10 or < 10) as collected on eCRF and on IRT

The following baseline disease characteristics will be summarized by treatment group for the randomized population:

- BILAG-2004 grade by organ system
- BILAG-2004 global score
- Categorization of BILAG-2004 A/B grades (at least one A, no A and at least 2 Bs, No A and < 2 Bs)
- SLEDAI-2K score
- SLEDAI-2K (\geq 10 or < 10)
- CLASI-A score
- swollen joint count
- tender joint count
- count of joints that are both tender and swollen (= active joints)

- Physician's Global Assessment of disease activity

Sponsor: Bristol-Myers Squibb
Protocol no: IM011021

